## **Background:**

Atrial fibrillation (AF) is the most common arrhythmia and its prevalence is projected to rise with the increase in age and comorbid disease in the patient population. AF is associated with significant morbidity and a nearly doubled risk of death.

As such the development of therapies which prevent or slow the progression of AF is imperative. In randomized controlled trials of therapies for AF, pharmacologic maintenance of sinus rhythm has not been demonstrated to be superior to therapies to control ventricular rates. In addition, medical therapy to maintain sinus rhythm was associated with significant cost and increased rates of hospitalization . However, in an "on treatment" analysis of the AFFIRM study which originally compared rhythm and rate control strategies, at an average of 3.3 years of follow up, the presence of sinus rhythm was associated with a significantly decreased risk of death (hazard ratio = 0.53). These findings suggest that the adverse effects of antiarrhythmic drugs in rate versus rhythm control studies offset the benefits of maintaining sinus rhythm when they are successful. Catheter ablation of the pulmonary veins and atria has been demonstrated to decrease the frequency of AF by 70-80% in several studies and provides a promising alternative to antiarrhythmic therapies.

Obesity is a known risk factor for AF and weight reduction through caloric reduction and exercise has been demonstrated to decrease the duration and symptomatic burden of AF in overweight and obese individuals in a randomized controlled trial. In a recently published retrospective cohort study of a physician led weight management intervention, successful reduction of 10% of body weight was associated with a six-fold increase in arrhythmia free survival. Similarly, in a cohort study of overweight and obese patients undergoing catheter ablation for AF, a program of aggressive risk factor management prior to ablation led to improved glycemic control, blood pressure reduction, favorable left atrial remodeling and a nearly fivefold increase in AF free survival at two years with less use of antiarrhythmic medications.

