#### **Trial Design:**

The proposed study will be a randomized control trial comparing metformin therapy to a control group in patients with a BMI  $\geq$ 27 and atrial fibrillation who have elected to undergo a rhythm control strategy with ablation. Upstream therapy with Metformin will be used in a randomized fashion. The only variation to the standard of care will be the addition of Metformin therapy and additional blood draws for safety monitoring and EKGs for measuring outcomes in both the intervention and control groups.

Patients meeting the below inclusion and exclusion criteria who provide informed consent will be randomized to control versus metformin therapy six weeks prior to rhythm control.

At baseline all study patients will be assessed for:

Age, Gender, Weight, BMI, Tobacco Use, Hypertension, Hemoglobin A1c, Hyperlipidemia, serum CRP, glomerular filtration rate estimating equation (eGFR), B12, liver function tests (AST, ALT, ALP, bilirubin, albumin, INR), lactic acid, History of Coronary Artery Disease by MI, PCI, or CABG, History of Valvular Disease, History of Obstructive Sleep Apnea, Type of AF and duration, Number of Antiarrhythmic Medications (not including beta-blockers or calcium channel blockers).

In addition, patients will fill out a survey to determine their Atrial Fibrillation Severity Score (AFSS) - a validated tool to assess the symptomatic burden of AF - and will receive education on dietary changes and exercise

Metformin will be initiated at 500 mg daily and increased as tolerated to 2000 mg daily over a three week period. Subjects will be instructed to hold Metformin on the day of any procedure or study requiring the administration of intravenous contrast and to resume 48 hours after the contrast administration and reinstituted only after renal function has been reevaluated and found to be at the patient's baseline. All patients will receive information on dietary changes to promote weight loss and will be encouraged to increase exercise activities. Patients will discontinue treatment at any time they are found to meet the baseline exclusion criteria for the study.

The initiation of the drug and the dosage increases will be overseen by a designee (mid-level cardiology practitioner) who will be responsible for stopping dosage increases if side effects occur. Six weeks after the initiation of drug the patient will undergo ablation with the intent of achieving rhythm control.

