#### **Outcomes and Assessment of Efficacy:**

The primary outcome by intention to treat analysis will be maintenance of sinus rhythm by chart review, EKG, and Atrial Fibrillation Severity Score at 3 and 6 months after the initial attempt at rhythm control.

Secondary outcomes will include hospitalization related to arrhythmic events or medication side effects, number of antiarrhythmic medications, number of repeat ablations, BMI, Hemoglobin A1c, and number of thromboembolic events.

Pre-specified subgroup comparisons will include comparing patients randomized to metformin who have a 5% reduction in weight at 6 months to all control patients who achieve a 5% reduction in weight, and to all control patients.

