#### **Statistics:**

We expect a 30% recurrence of AF after patients undergo ablation. After ablation, we expect the recurrence of AF to be 30% less in the intervention group of patients on metformin than the control group.

Using an 80% power at a 95% confidence interval, the sample size of the control group (ablation only) and the intervention group (ablation plus metformin) will be 400 each for a two tailed study, accounting for up to a 3% attrition rate in each group. The total sample size of this study will be 800. It is estimated to take five years to accrue subjects.

Statistical methods employed to analyze outcomes will be a Pearson's  $X^2$  test for categorical variables. Analysis of Variance will be used for continuous variables. All tests are two-sided and P < .05 will be used to indicate a statistically significant difference.

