### **Ethics:**

This study will be conducted in accordance with Good Clinical Practice (GCP), as defined by the International Conference on Harmonization (ICH) and in accordance with the ethical principles the United States Code of Federal Regulations, Title 21, Part 50 (21CFR50).

The study will be conducted in compliance with the protocol. The protocol and any amendments and the subject informed consent will receive Institutional Review Board (IRB) approval prior to initiation of the study.

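### Comparing metformin patients who lost 5% of weight with all controls selects one arm on a post-randomisation variable; if weight loss goes with less AF recurrence, it favours metformin even when the drug is inert

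*Combined protocol and SAP*

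**What the plan says.** The Outcomes and Assessment of Efficacy section names an intention-to-treat primary outcome and a list of secondary outcomes. A further sentence begins "Pre-specified subgroup comparisons will include" and describes "comparing patients randomized to metformin who have a 5% reduction in weight at 6 months" with two comparators: "to all control patients who achieve a 5% reduction in weight, and to all control patients". This gives two contrasts:

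- (a) metformin weight-losers versus control weight-losers;
- (b) metformin weight-losers versus the entire control arm.

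The section names neither an endpoint nor a test for them. The Statistics section offers Pearson's chi-square and analysis of variance, and closes with a general rule: "All tests are two-sided and P < .05 will be used to indicate a statistically significant difference". Nothing in the document calls contrast (b) exploratory, adjusts it or limits how it may be read.

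Two other places matter. The Background links weight loss to less AF, for example "successful reduction of 10% of body weight was associated with a six-fold increase in arrhythmia free survival". Trial Design gives lifestyle advice to both arms: "All patients will receive information on dietary changes to promote weight loss and will be encouraged to increase exercise activities".

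**The concern.** Randomisation takes place six weeks before ablation, and the weight that defines the subgroup is recorded at the 6-month follow-up. Membership is therefore settled after treatment assignment. Contrast (b) applies the filter to one arm only. Controls get the same diet and exercise advice, so some of them may also lose 5%, but here they stay pooled with the controls who did not.

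If losing 5% is associated with less recurrence, for whatever reason, contrast (b) sets a better-prognosis part of one arm against the whole of the other. The difference is then partly or wholly selection. At stake is a planned comparison, read at P < .05, that reports a metformin benefit which randomisation does not support. Planning it in advance does not remove the bias and may lend the result credibility.

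**Working it through.** **Inputs from the Statistics section.** Control recurrence 30%; a 30% relative reduction, so 30% × 30% = 9 points and 21% on metformin; 80% power; two-sided 5%; 400 per arm including 3% attrition.

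**The plan's own figure.** For 0.30 versus 0.21 the mean is 0.255.

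- Uncorrected: n = [1.96·√(2·0.255·0.745) + 0.8416·√(0.30·0.70 + 0.21·0.79)]² / 0.09² = 367.
- With continuity correction: 389. Dividing by 0.97 gives 402, which agrees with the stated 400 to within rounding.

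Evaluable patients per arm: 400 × 0.97 = 388.

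**Assumptions the documents do not supply.**

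- The comparison is on AF recurrence.
- Metformin affects neither weight nor AF.
- The same share f of each arm loses 5%, with f from 10% to 35%.
- The relative risk (RR) of recurrence in weight-losers versus others ranges from 1.0 to 0.5.

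**Size of the bias.** Let p_L and p_N be recurrence in weight-losers and others, with p_L = RR·p_N and overall recurrence 0.30. Then p_N = 0.30/(f·RR + 1 − f), and the expected difference in contrast (b) is

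p_L − [f·p_L + (1 − f)·p_N] = −(1 − f)(p_N − p_L).

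This is negative, so it favours metformin, whenever p_L < p_N.

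Example, f = 25% and RR = 0.7: p_N = 0.30/0.925 = 0.324 and p_L = 0.227, a gap of 0.300 − 0.227 = 7.3 points.

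**Chance of a false benefit.** Each scenario used 200,000 simulated trials and the uncorrected Pearson test. A result counts when two-sided P < .05 and the direction favours metformin (nominal 2.5%).

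| RR in weight-losers | f = 10% | f = 15% | f = 25% | f = 35% | Gap at f = 25% (points) |
|---|---|---|---|---|---|
| 1.0 | 2.2% | 2.3% | 2.3% | 2.4% | 0 |
| 0.95 | 3.1% | 3.5% | 3.9% | 3.9% | 1.1 |
| 0.9 | 4.5% | 5.3% | 6.1% | 6.2% | 2.3 |
| 0.8 | 9.2% | 11.6% | 14.0% | 14.6% | 4.7 |
| 0.7 | 17.4% | 22.8% | 28.6% | 30.3% | 7.3 |
| 0.5 | 46.9% | 61.1% | 74.5% | 78.5% | 12.9 |

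The favourable-tail rate reaches 5% at RR 0.89 for f = 10%, and at about 0.92 for f = 25% or 35%.

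**Hand check of one cell (f = 25%, RR 0.7).** There are 388 × 0.25 = 97 weight-losers.

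- Pooled rate: (97·0.227 + 388·0.300)/485 = 0.285.
- Null standard error: √(0.285·0.715·(1/97 + 1/388)) = 0.0513.
- Standard error under the assumed rates: √(0.227·0.773/97 + 0.30·0.70/388) = 0.0485.
- (1.96·0.0513 − 0.0730)/0.0485 = 0.57, an upper-tail probability of about 28.5%, against 28.6% simulated.

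**The other contrasts under the same null.** Weight-losers versus weight-losers: 2.5–2.6% in favour, 4.9–5.2% two-sided. Whole arms: 2.4% in favour, 4.9% two-sided. The inflation therefore comes from filtering one arm only.

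**The case against.** The strongest reply is that little rests on contrast (b). It is a subgroup comparison placed after the primary and secondary outcomes, the trial is sized on the whole arms, and no section makes it a basis for an efficacy claim. The same sentence also includes the like-for-like contrast (a), so a selection artefact would tend to appear in (b) but not in (a). This limits the severity. It does not repair (b): contrast (a) is smaller and less precise, and the plan does not say how to read the two together if they disagree.

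The size also cannot be established from the documents. The Background figures concern a 10% loss in a retrospective cohort, a diet and exercise trial, and multi-factor risk management. None gives a relative risk for a 5% loss, or for loss on a drug. That stands, and the results run from no inflation to severe inflation.

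The direction is an assumption too. If weight loss marked a worse prognosis, the bias would run against metformin: at RR 1.25 and f = 25%, p_L = 1.25 × 0.30/1.0625 = 0.353, a 5.3-point gap against the drug with 18% two-sided rejection. The favourable direction is the protocol's own expectation; in neither case does (b) estimate a drug effect.

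Finally, the 5% rate at RR 0.92 doubles only the favourable tail. The two-sided rate there is about 6.1% against 5%. And because no endpoint or test is named for the subgroups, reading them at P < .05 relies on the general rule in the Statistics section, which does cover all tests.

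**Conclusion.** The concern holds. As written, contrast (b) selects one arm on a post-randomisation variable, and the plan carries no caveat. Given that 5% weight loss goes with less recurrence, the direction of the bias follows from the algebra and does not depend on f.

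Its size is conditional. It is negligible near RR 1. At RR 0.7 and f = 25% the spurious gap of 7.3 points is about four-fifths of the 9-point design effect (7.3/9 = 0.81). At RR 0.5 the gap of 12.9 points exceeds it. All of this assumes an inert drug, 388 evaluable per arm, 30% overall recurrence and recurrence as the endpoint.

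The intention-to-treat primary analysis and the sample size are not affected, so this is a change that should be made rather than one on which the trial's validity depends.

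**What to change.** In Outcomes and Assessment of Efficacy:

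1. Delete the comparison of metformin weight-losers with all controls, or keep it as a descriptive, non-causal summary without a P value. Either removes the risk of misreading it at P < .05.
2. Label the comparison of weight-losers with weight-losers exploratory. It keeps its error rate if metformin changes nothing, but randomisation no longer protects it if metformin changes who loses weight, and the direction of that bias is unknown.
3. State that any efficacy conclusion rests on the whole randomised arms.

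If the role of weight loss is of real interest, a pre-specified mediation or principal-stratum analysis, with its assumptions stated, would address it more directly; this is optional.

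The cost is a wording amendment. The Ethics section requires that "The protocol and any amendments and the subject informed consent will receive Institutional Review Board (IRB) approval", so it goes to the IRB. It needs no new data, visits or patients, and is best made before outcomes are analysed.

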#### **Assessment of Safety:**

A Medical Monitor will be utilized to provide general oversight and safety considerations for this study. The Medical Monitor will provide advice to the Sponsor-Investigator regarding actions the committee deems necessary for the continuing protection of subjects enrolled in this study. The Medical Monitor will be charged with assessing such actions in light of an acceptable risk/benefit profile for metformin. The Medical Monitor will act in an advisory capacity to the Sponsor-Investigator and will monitor subject safety data for the study.

All patients included in the study will have monitoring of renal function, hepatic function, and serum lactic acid at baseline, at the time of ablation or initiation of rhythm control, and at 3-month and 6-month follow ups. This data will be reviewed by an investigator who is not involved in the outcome analysis. This investigator will be a mid-level who will be assigned to check the routine labs. The parameters for immediate reporting to one of the study coordinators are the following- creatinine greater than or equal to 1.5 in males or 1.4 in females, elevated lactic acid, or serum bilirubin >1.5x the upper limit of normal. Exclusion criteria will also be reviewed at each follow up, and if at any point a patient meets the exclusion criteria for the study or has an unexpected adverse event they will be withdrawn from the study.

Routine reports will be provided to the Medical Monitor every 2 months and will include rates of disenrollment, reason for disenrollment, unexpected adverse events, and mortalities. If a statistically significant harm is detected in the analysis of the safety data collected at 2 month intervals the protocol will be terminated.

Adverse events will be solicited at routine follow-up with a designee and are defined as follows: .

Lactic Acidosis – lactic acid >2.1 mmol/L as measured at either routine follow up or if measured during a hospitalization for any reason

Thromboembolic event – any stroke, mesenteric ischemia, limb ischemia, or other event determined to be of an embolic etiology secondary to atrial fibrillation Vitamin B12 levels and any change from baseline at the 3 and 6 month timepoints will be measured and submitted.

Adverse events will be reviewed every 2-months and a statistical analysis will be done. If the analysis finds that any of these adverse events have occurred more frequently in either group in a statistically significant manner, the trial will be stopped.

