Patients will be followed up in regular intervals after the initial attempt at rhythm control. The minimum follow up interval is every three months. More frequent follow up may be scheduled as deemed necessary by the treating physician.

[figure not shown]
At the time of the first attempt at rhythm control, at the 3 month follow up, and at the 6 month follow up all study patients will be assessed again for:

Weight, BMI, Hemoglobin A1c, serum CRP, eGFR, liver function tests (AST, ALT, ALP, bilirubin, albumin, INR), B12, lactic acid, number of antiarrhythmic agents, presence of AF by EKG, and Atrial Fibrillation Severity Score.

At each 3-month and 6-month follow up, data will be reviewed by a designee who will use the criteria described below for reporting to the Medical Monitor. The patient will also be assessed for the occurrence of any adverse events as defined below and adverse events will be reported to the medical monitor.

At the end of 6 months of therapy, the decision to continue Metformin beyond 6 months will be made in conjunction with the patient's treating cardiologist and primary care physician.

Figure 1.

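### Patients who meet an exclusion criterion or have an unexpected adverse event leave the study, and nothing secures their rhythm outcome for the intention-to-treat analysis

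*Combined protocol and SAP*

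**What the plan says.** - **Assessment of Safety.** "Exclusion criteria will also be reviewed at each follow up", and a patient who at any point "meets the exclusion criteria for the study or has an unexpected adverse event they will be withdrawn from the study". The two-monthly reports to the Medical Monitor cover "rates of disenrollment, reason for disenrollment, unexpected adverse events, and mortalities", so leaving the study is treated as a real event.
- **Trial Design.** For the exclusion criteria the rule is different: "Patients will discontinue treatment at any time they are found to meet the baseline exclusion criteria for the study". Leaving the study is not mentioned, and neither are unexpected adverse events. The section also schedules rhythm assessment at the first rhythm-control attempt and at 3 months, and "at the 6 month follow up all study patients will be assessed again".
- **Outcomes and Assessment of Efficacy.** "The primary outcome by intention to treat analysis will be maintenance of sinus rhythm", determined "by chart review, EKG, and Atrial Fibrillation Severity Score at 3 and 6 months after the initial attempt at rhythm control".
- **Study Drug Compliance.** Temporary discontinuation of study drug is foreseen, so an off-drug status short of study exit already exists. It is not linked to the withdrawal triggers.
- **Statistics.** 400 patients per arm, 30% recurrence after ablation, recurrence 30% less on metformin, and up to 3% attrition per group. There is no rule for missing outcomes.

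**The concern.** An intention-to-treat comparison needs the outcome of every randomised patient. Here a safety rule removes some of them after randomisation, possibly before the 6-month assessment, and no text keeps their outcome. The 3% allowance protects the sample size. It does not protect comparability between the arms.

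Withdrawal could be linked to arm in at least two ways. Controls have ablation only, so an unexpected event caused by the drug can arise only on metformin. In the other direction, a diagnosis of diabetes is an exclusion criterion, and the Potential Benefits section says metformin reduces progression from prediabetes to diabetes; that trigger could fire more often in controls. The documents do not say how often either would happen within the study period.

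A link to rhythm is less certain. The plan does not define an unexpected adverse event. If the term covers a thromboembolic event, whose definition includes any "other event determined to be of an embolic etiology secondary to atrial fibrillation", then withdrawal is tied to AF itself.

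If withdrawal depends on these things, the remaining patients may no longer be comparable, and the difference in recurrence can be biased in either direction.

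**Working it through.** **Inputs.** From Statistics: 400 per arm, control recurrence 30%, two-sided 5% level, Pearson chi-squared test, 3% attrition. Reading 30% less as a relative reduction gives 0.30 × 0.70 = 21% on metformin. Statistics does not say whether the 3% includes the safety withdrawals. Every other withdrawal rate, and every recurrence rate among withdrawn patients, is an assumption.

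**The plan's own figure.** For 30% v 21%, 80% power and a two-sided 5% level, the continuity-corrected formula gives 389 per arm; 389/0.97 = 401.03, so 402, against 400 stated. This reproduces the plan to within 2 patients. Without continuity correction, power is 83.3% with 400 per arm and 82.1% with 388 (3% lost, unrelated to rhythm).

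**Method.** Let *p* be true recurrence in an arm, *w* the share withdrawn with no outcome, and *r* recurrence among those withdrawn. Among the patients left:

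- observed recurrence = (*p* − *w r*)/(1 − *w*)
- remaining n = 400(1 − *w*)

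Error rates and power use the pooled two-proportion test (normal approximation).

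**1a. Plan's attrition, no true effect.** *w* = 0.03 in both arms (12 of 400, leaving 388) and *p* = 0.30 in both. One arm has *r* = 0.40, 0.50 or 0.60; the other has *r* = 0.30. For *r* = 0.40: (0.30 − 0.03 × 0.40)/0.97 = 0.288/0.97 = 29.7%.

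| *r* in one arm | Observed, that arm v other | Bias (points) | Type I error |
|---|---|---|---|
| 0.40 | 29.7% v 30.0% | 0.31 | 5.1% |
| 0.50 | 29.4% v 30.0% | 0.62 | 5.4% |
| 0.60 | 29.1% v 30.0% | 0.93 | 5.9% |

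With *r* = 0.30 in both arms there is no bias and the error is 5.0%. Any value of *r* and *w* common to both arms also gives no bias when there is no true effect.

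**1b. Plan's attrition, true 30% v 21%.** The arm without the excess has *r* equal to its own true rate (21% for metformin, 30% for control). The true difference is 9 points, and power is 82% if withdrawal is unrelated to rhythm.

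| *r* in the arm with the excess | Excess in control: difference, power | Excess in metformin: difference, power |
|---|---|---|
| 0.40 | 8.69 points, 80% | 9.59 points, 87% |
| 0.50 | 8.38 points, 77% | 9.90 points, 89% |
| 0.60 | 8.07 points, 74% | 10.21 points, 91% |

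The two columns are not like for like: these values of *r* lie 10, 20 and 30 points above the control rate but 19, 29 and 39 points above the metformin rate.

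**2. Heavier withdrawal, no true effect.** In one arm, 10, 15 or 20% of recurrent patients are withdrawn; 5% of everyone else is withdrawn, in both arms. For 10%: *w* = 0.30 × 0.10 + 0.70 × 0.05 = 0.065; *r* = 0.030/0.065 = 0.46; observed = (0.30 − 0.030)/0.935 = 28.9%.

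| Recurrent patients withdrawn | *w* v other arm | n v n | Observed v other arm | Bias (points) | Type I error |
|---|---|---|---|---|---|
| 10% | 6.5% v 5% | 374 v 380 | 28.9% v 30.0% | 1.12 | 6.3% |
| 15% | 8.0% v 5% | 368 v 380 | 27.7% v 30.0% | 2.28 | 10.6% |
| 20% | 9.5% v 5% | 362 v 380 | 26.5% v 30.0% | 3.48 | 18.3% |

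**3. Half of the withdrawn patients still supply the 6-month outcome.** All withdrawal shares are halved. Case 1a falls to 0.15, 0.30 and 0.46 points, with type I error 5.0, 5.1 and 5.2%. Case 2 falls to 0.54, 1.09 and 1.65 points, with type I error 5.3, 6.3 and 8.0%.

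**The case against.** The best reply is that the plan can be read harmoniously. Trial Design stops treatment only, the primary analysis is by intention to treat, and assessments are scheduled for all study patients; withdrawal in a safety section may be loose wording for stopping the drug. This is possible for the exclusion criteria. It is weaker for unexpected adverse events, on which Trial Design is silent, and it sits badly with the reporting of disenrollment. A site that follows the safety text literally would stop follow-up.

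Second, some outcomes would survive. Chart review is a named source, and a trigger first found at the 6-month visit costs no scheduled assessment. This stands and reduces the loss, but no text extends chart review past withdrawal.

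Third, the mechanisms are uncertain, and much of this stands. Thromboembolic events are solicited and counted as a secondary endpoint, so they are hard to call unexpected; the AF qualifier may also attach only to the last item in their definition. The gastrointestinal effects are described as known, and lactic acidosis as very rare. Both arms undergo ablation, so unexpected events can arise in either.

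Fourth, the effect at 3% attrition is small, and the large figures need withdrawal rates that nothing in the documents supports. That is correct. The case for change rests on the contradiction between the rules and on how cheaply it can be removed, not on a predicted bias.

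**Conclusion.** The concern holds and should be fixed. It is certain from the text that the safety rule ends study participation, that Trial Design has a different rule for the exclusion criteria, and that nothing secures the rhythm outcome after withdrawal. As written, the intention-to-treat analysis may not be possible in full.

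The size and direction of any bias are unknown. Within the plan's 3% attrition, the effect on bias and type I error is small under the assumed recurrence rates, although power can fall below the planned 80% if the excess recurrence is among withdrawn controls. The larger figures apply only if withdrawals exceed 3% and depend on rhythm in one arm.

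**What to change.** 1. Reconcile Trial Design, Assessment of Safety, and Outcomes and Assessment of Efficacy, so that ending study drug is stated separately from ending follow-up. The clinical stopping rules, including those for an unexpected adverse event, remain for the sponsor to set.
2. State that every randomised patient, including one who has stopped study drug or met a withdrawal trigger, keeps the planned 3- and 6-month rhythm assessments (EKG, chart review and AFSS) unless consent is withdrawn, and is analysed in the randomised arm.
3. Add a sensitivity analysis for outcomes still missing. One option is a tipping-point analysis that varies the assumed recurrence among missing patients separately in each arm.
4. Secondary: define an unexpected adverse event, and report drug stops and study exits separately by arm to the Medical Monitor, who already receives disenrollment rates and reasons.

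The cost is protocol and analysis wording, plus a small amount of continued follow-up at visits already planned. The documents give no cost figure. The change is best made before patients are withdrawn, because an EKG or AFSS not obtained at the time may not be recoverable.

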### Potential Risks:

Per the Glucophage (metformin) package insert, metformin does not cause hypoglycemia in individuals with diabetes mellitus or normal subjects except in certain circumstances excluded by the study's exclusion criteria.

Metformin does have a warning for the risk of lactic acidosis. Per the insert:

The reported incidence of lactic acidosis in patients receiving metformin hydrochloride is very low (approximately 0.03 cases/1000 patientyears, with approximately 0.015 fatal cases/1000 patientyears). In more than 20,000 patient-years exposure to metformin in clinical trials, there were no reports of lactic acidosis. Reported cases have occurred primarily in diabetic patients with significant renal insufficiency, including both intrinsic renal disease and renal hypo perfusion, often in the setting of multiple concomitant medical/surgical problems and multiple concomitant medications.

In a more recent review of pooled data from 347 trials and cohort studies an estimated risk of 4.3 cases of lactic acidosis in 100,000 patient years was calculated and this risk was equivalent with other antihyperglycemic agents. The ultimate conclusion of this investigation was "There is no evidence to date that metformin therapy is associated with an increased risk of lactic acidosis or with increased levels of lactate compared with other antihyperglycemic treatments if the drugs are prescribed under study conditions, taking into account contraindications". 26

Other known adverse reactions to metformin therapy include gastrointestinal side effects which include flatulence, diarrhea, nausea and vomiting, and abdominal discomfort. These symptoms are dose dependent and can be relieved by dose reduction. Approximately 50% of all patients can tolerate a maximal dose of metformin but a small minority of around 5% cannot tolerate any dose of metformin.

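### Gastrointestinal reactions are outside the solicited adverse-event definition, so symptoms short of hospitalization, disenrollment or a stopped dose increase cannot be compared systematically between arms

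*Combined protocol and SAP*

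**What the plan says.** The protocol's Assessment of Safety section says "Adverse events will be solicited at routine follow-up with a designee and are defined as follows". Two entries follow: "Lactic Acidosis – lactic acid >2.1 mmol/L as measured at either routine follow up or if measured during a hospitalization for any reason" and "Thromboembolic event – any stroke, mesenteric ischemia, limb ischemia, or other event determined to be of an embolic etiology secondary to atrial fibrillation". Vitamin B12 is mentioned next, where levels and "any change from baseline at the 3 and 6 month timepoints will be measured and submitted". That is a laboratory reporting item, not a defined adverse event.

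Two other places rely on this definition. Trial Design has patients assessed at 3 and 6 months for adverse events and points forward to the definition. The closing paragraph of Assessment of Safety has a review every two months and stops the trial if "any of these adverse events have occurred more frequently in either group in a statistically significant manner".

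Potential Risks states: "Other known adverse reactions to metformin therapy include gastrointestinal side effects which include flatulence, diarrhea, nausea and vomiting, and abdominal discomfort". It calls these reactions dose dependent, says that lowering the dose can relieve them, and adds: "Approximately 50% of all patients can tolerate a maximal dose of metformin but a small minority of around 5% cannot tolerate any dose of metformin".

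Outcomes and Assessment of Efficacy includes among the secondary outcomes "hospitalization related to arrhythmic events or medication side effects".

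**The concern.** The protocol names gastrointestinal symptoms as known reactions to the study drug, yet its working definition of an adverse event leaves them out. A site following the text would ask about lactate and emboli at each visit. It would have no instruction to ask either arm about diarrhea, nausea or abdominal discomfort.

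Two things are at stake. First, Assessment of Safety asks the Medical Monitor to judge whether metformin's balance of risk and benefit is acceptable, and the final report will have to do the same. Neither would have a two-arm table of these known reactions. Second, dosing is as tolerated and the primary analysis is by intention to treat. If the efficacy result is weak, readers will ask how many patients had escalation stopped and why, and no planned record is described for the reason.

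**Working it through.** **Does any part of the plan collect these symptoms in both arms?**

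- Solicited definition (Assessment of Safety): lactic acidosis and thromboembolism. No gastrointestinal item.
- Visit assessment (Trial Design): tied to that definition.
- Two-monthly between-group test (Assessment of Safety): limited to the same events by its back-reference.
- Hospitalization for medication side effects (Outcomes and Assessment of Efficacy): both arms, but only events leading to admission.
- Disenrollment rates and reasons (Assessment of Safety): reach the Medical Monitor every two months, but miss a patient who stays in the study with symptoms or on a lower dose.
- Unexpected adverse events (Assessment of Safety): a reaction the protocol lists as known would not ordinarily qualify.
- Titration oversight (Trial Design): a designee stops dose increases when side effects occur. This covers the metformin arm only, with no stated record or analysis.
- Drug accountability (Study Drug Compliance): gives exposure, not symptoms or reasons.

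No route collects symptoms short of admission or withdrawal in the same way in both arms.

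**Plan's sample size.** Inputs from Statistics: 30% recurrence in controls; 30% less on metformin, read as relative, so 0.30 × 0.70 = 21%; two-sided 0.05; 80% power; 3% attrition.

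- Uncorrected: n = [1.96√(2 × 0.255 × 0.745) + 0.8416√(0.30 × 0.70 + 0.21 × 0.79)]² / 0.09² = 367 per arm.
- With continuity correction: (367/4) × [1 + √(1 + 4/(367 × 0.09))]² = 389 per arm.
- With attrition: 389/0.97 = 401.03, rounded up to 402.

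This agrees closely with the stated 400 per arm, which is used below.

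**Scale.** This assumes that the general percentages in Potential Risks apply to this non-diabetic sample.

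- Not tolerating the maximal dose: 400 × (1 − 0.50) = 200.
- Tolerating no dose: 400 × 0.05 = 20.

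For contrast, 400 patients followed for 6 months give 200 patient-years; adding the 6 weeks before ablation gives 400 × 32/52 = 246. At the quoted 0.03 per 1000 patient-years, the expected number of lactic acidosis cases is 0.006 to 0.007. At the other quoted rate, 4.3 per 100,000, it is 0.009 to 0.011. The protocol's lactate threshold may count more patients than these reported-case rates.

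**Precision if symptoms were collected.** The 95% half-width for a difference with rate p in both arms is 1.96√(2p(1 − p)/400). The documents give no gastrointestinal event rates, so p is assumed.

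- p = 10%: 1.96√(0.18/400) = 4.2 points.
- p = 50%: 1.96√(0.50/400) = 6.9 points.

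The half-widths for one arm alone are smaller (2.9 and 4.9 points) but do not describe the comparison.

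**Is sample size the obstacle?** Take 400 × 0.97 = 388 evaluable per arm, two-sided 0.05, no continuity correction, and assumed control rates of 5% to 20%. Power for a 10-point difference runs from 99.7% (5% against 15%) to 89.7% (20% against 30%). For a 5-point difference it runs from 75.4% to 38.5%. Large differences would be detectable; the gap is in what is collected.

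**The case against.** The definition is not cleanly closed. Assessment of Safety also uses the term for unexpected events, and Treatment of Subjects lists occurrence of adverse events at the ablation, 3-month and 6-month visits without pointing to the definition. A site might read the term broadly. This stands as an inconsistency, but neither place offers another definition or lists symptoms to ask about, and the between-group test refers to the two defined events.

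A reader might infer that gastrointestinal reactions will not be captured at all, or that tolerability cannot be compared in any way. The documents do not support that. Admissions for medication side effects can be compared between arms, and the Medical Monitor would see disenrollments for intolerance.

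A reader might also infer that nothing could explain an efficacy result diluted by low doses. That too goes further than the text. Drug accountability at each visit, reporting of interruptions of 7 consecutive days or more, and titration oversight should let the dose reached be largely reconstructed. What may be lost is the reason an increase was stopped.

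Finally, tolerability is not a stated objective, and the primary result does not depend on this point. Both are true and limit its weight. They do not answer the gap, because the protocol itself asks for a risk-benefit judgment.

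**Conclusion.** The point holds in a limited form. Followed as written, the plan gives an incomplete safety comparison: gastrointestinal symptoms that do not lead to admission, disenrollment or a stopped dose increase have no planned collection, and none of the incidental routes gives a systematic two-arm comparison of symptoms. It is worth correcting, and it leaves the primary analysis untouched.

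The counts of about 200 and 20 rest on carrying general tolerance percentages over to non-diabetic patients. They should not be read as numbers of uncounted gastrointestinal events. The precision of 4.2 to 6.9 points rests on the assumed equal rates of 10% and 50% and on all 400 patients per arm being assessed.

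**What to change.** - **Two-arm list.** Add to Assessment of Safety a separate list of expected reactions: flatulence, diarrhea, nausea, vomiting and abdominal discomfort. Ask the same questions in both arms at the ablation, 3-month and 6-month visits, and report the results by arm.
- **Metformin arm only.** Record the daily dose reached and the reason any increase was stopped. Note symptoms at the titration contacts the designee already oversees, since the dosing schedule reaches its last step in week 4 and ablation is at six weeks. Keep these notes out of the between-arm table, because controls have no matching contacts.
- **Stopping statements.** Assessment of Safety has two: one tied to the defined adverse events, and a broader one tied to any statistically significant harm in the safety data. The sponsor should say how the new list relates to each and reconcile them, so that descriptive tabulation of an expected reaction does not end the trial unintentionally. Which rule should apply is for the sponsor to decide.
- **Starting dose.** Trial Design and Storage and Dispensing start at 500 mg daily, while Treatment of Subjects has one 500 mg tablet twice a day. These must be reconciled, because the tolerability data depend on the titration.

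The cost is a few questions at visits already scheduled, one more table and a small data-entry burden. Because no placebo is described, self-reported symptoms carry reporting bias, and the table should say so.
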